8.10. Concomitant Medications

Concomitant medications are defined as non-study medications that are started after the initiation but before the end of the study treatment (last dose of study drug + 28 days, death, whichever earlier), or started before the initiation of the study treatment and ended or remain ongoing after the study treatment initiation. Concomitant medications will be coded in WHO drug dictionary (March 2018 version, or higher). Medication not in the WHO drug dictionary will be classified as “Not Coded” in the analysis.

The ATC coding scheme of the WHO will be used to group medications into relevant categories. A frequency table by ATC class and preferred name will be provided. All concomitant medications documented on the CRF will be listed for the ITT population.

9. STUDY TREATMENTS AND EXTENT OF EXPOSURE

9.1. Treatment Duration

See Section 5.1 for cycle start and end date as well as cycle number calculation.

The treatment duration (months) is defined as:

$$[(\text{The treatment duration end date}) - (\text{the first study drug start date}) + 1] / 30.4375,$$

where treatment duration end data is defined as the last dose date + 7 days (the prescribed rest period of each cycle), or the death date, whichever is earlier.

Summary statistics will be provided for treatment duration by treatment group.

By-subject listings of all exposure information collected on the CRF will be provided.

9.2. Number of Treatment Cycles

Number of cycles for each treatment group will be summarized both descriptively and categorically for the safety population by treatment group.

9.3. Duration of Exposure

Duration of exposure will be calculated for each treatment group. Duration of exposure (days) of a study drug is defined as the total number of days on the study drug during the treatment period (excluding the periods of dose break per protocol or dose interruptions). Duration of exposure will be summarized descriptively for the safety population.

9.4. Average Length of Cycle

The average length of cycle (days) is defined as the treatment duration (in days) divided by the number of cycles. The average length of cycle (days) will be summarized descriptively for the safety population by treatment group.

9.5. Average Number of Days Dosed per Cycle

The average number of days dosed per cycle is defined as the number of days a subject is dosed divided by the number of cycles the subject had. The average number of days dosed per cycle will be summarized descriptively for the safety population by treatment group.

9.6. Cumulative Dose

The cumulative dose (mg) for a study drug is defined as the sum of all doses taken during the treatment period (in mg). Cumulative dose will be summarized for the safety population by treatment group.

9.7. Average Daily Dose

Average daily dose (mg/day) of a study drug is defined as the cumulative dose of the study drug divided by the number of days dosed (received a non-zero dose). Average daily dose will be summarized for the safety population by treatment group.

9.8. Dose Intensity

Actual dose intensity (mg/day) during the treatment is defined as the cumulative dose divided by treatment duration, which is defined as in Section 9.1.

Relative dose intensity (RDI) is defined as the ratio of actual dose intensity to the planned dose intensity, which is $300\text{mg/day} \times 21 \text{ days}/28\text{days} = 225 \text{ mg/day}$ for all subjects.

The overall relative dose intensity will be categorized into $< 75\%$, 75% to 85% , 85% to 100% , and $> 100\%$, and frequency counts will be provided by treatment group.

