8.2 Treatment Administration and Schedule

As of Amendment 3.0, all subjects in Cycles 1 or 2 will receive CC-486 for 14 days of a 28-day cycle schedule. Subjects may increase to a 21-day schedule at the conclusion of Cycle 2 if there are no Grade 3 or 4 toxicities requiring dose delay or reductions and if there is no evidence of hematological improvement upon discussion and agreement between investigator and the Medical Monitor. Subjects remaining beyond Cycle 2 will continue to receive 300 mg oral azacitidine or matching placebo QD for 21 days of each 28-day treatment cycle as described in [Section 8.3](#). In the event of toxicity, dose and schedule may be modified (see [Section 8.2.4](#)). Subjects may continue to receive the protocol-prescribed therapy for as long as they benefit from the treatment or until treatment is discontinued for reasons detailed in [Section 12](#). The decision to discontinue a subject, which will not be delayed or refused by the sponsor, remains the responsibility of the treating physician. However, prior to discontinuing a subject, the investigator may contact the Medical Monitor and forward appropriate supporting documents for review and discussion.

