8.2.4 Dose Modifications

All subjects in Cycle 1 or 2 will receive CC-486 for 14 days of a 28-day cycle schedule. Subjects may increase to a 21-day schedule (Level +1) at the conclusion of Cycle 2 if no Grade 3 or 4 toxicities requiring dose delay or reductions and if no evidence of hematological improvement upon discussion and agreement between the investigator and the Medical Monitor.

When the dose level is adjusted, weekly hematology monitoring is required for 2 cycles including the cycle in which the adjusted dose or dosing schedule was applied as well as the following cycle, see Section 8.2.5 Re-treatment Criteria.

The dose/treatment schedule modifications steps for 14 days schedule are:

	Dose/schedule		
	300 mg/21d		Level +1
Dose escalation step	300 mg/14d		Level 1
Dose escalation step	200 mg/14d	Dose reduction step	Level -1
Dose escalation step	200 mg/7d	Dose reduction step	Level-2

All efforts should be made to dose IP according to schedule without cycle delay, dose interruption and reduction. Subjects will be monitored for hematologic toxicity and non-hematologic toxicity with the National Cancer Institute (NCI) Common Terminology Criteria for Adverse Events (CTCAE, Version 4.0) used as a guide for the grading of severity.

If a certain level of toxicity is observed (eg, [Table 2](#)) and considered by the investigator to be at least possibly related to treatment, IP dosing may be interrupted, delayed or modified. The investigator may contact the Medical Monitor prior to any treatment adjustment. Please note that in the event neutropenia Grade 4 is observed, or any adverse event that would put a subject at unacceptable risk in the investigator’s opinion, IP dosing may be interrupted, delayed or modified even if not considered by the investigator to be at least possibly related to treatment.

A maximum of one dose reduction step to 200 mg is permitted in the event of toxicity. A maximum of two treatment schedule modifications, stepwise first from 21 to 14 days and then from 14 days to 7 days, at a dose of 200 mg once a day are permitted in the event of continuing toxicity. Subjects are not allowed to receive less than 200 mg IP or be scheduled to receive treatment for less than 7 days.

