9.9. Dose Adjustment

Dose adjustment (reduction/interruption), as reported in the Study Drug Record CRF page, will be summarized by treatment group and include the following:

- Subjects with at least one dose adjustment
- Reason for dose adjustment
- Time to the first dose adjustment
- Time to the first dose adjustment due to AE
- Duration of the first dose adjustment due to AE

Subjects who have been assigned to 300 mg x 14 days dose during Cycle 1 or Cycle 2 and subjects who have not been assigned to 300 mg x 14 days dose during Cycle 1 or Cycle 2 will be identified and the number of subjects will be presented by treatment group.

For subjects who have not been assigned to 300 mg x 14 days dose during Cycle 1 or Cycle 2, the number of dose reductions will be identified and summarized by treatment group:

- Subjects with only one dose reduction (from 300 mg x 21 days to 200 mg x 21 days);
- Subjects with only two dose reductions (from 300 mg x 21 days to 200 mg x 21 days, then from 200 mg x 21 days to 200 mg x 14 days);
- Subjects with three dose reductions (from 300 mg x 21 days to 200 mg x 21 days, then from 200 mg x 21 days to 200 mg x 14 days, then from 200 mg x 14 days to 200 mg x 7 days).

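### Relative dose intensity is scaled to 225 mg/day for every subject, so full compliance on the 14-day schedule scores below 100%; the fixed 7-day closing rest separately shortens treatment duration and partly hides this

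*SAP*

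**What the plan says.** SAP 9.8 states: "Relative dose intensity (RDI) is defined as the ratio of actual dose intensity to the planned dose intensity". It gives the numerator: "Actual dose intensity (mg/day) during the treatment is defined as the cumulative dose divided by treatment duration". The denominator is 300 mg x 21/28 = 225 mg/day, applied to all subjects. Results are tabulated by arm as below 75%, 75 to 85%, 85 to 100% and above 100%.

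SAP 9.1 ends treatment duration at "the last dose date + 7 days (the prescribed rest period of each cycle), or the death date", whichever comes first. SAP 9.4 divides the same duration by the number of cycles to give average cycle length.

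Protocol 8.2 says: "As of Amendment 3.0, all subjects in Cycles 1 or 2 will receive CC-486 for 14 days of a 28-day cycle schedule". Protocol 8.2.4 repeats this and makes the increase to 21 days after Cycle 2 conditional. Protocol Section 6 and Table 1 footnote a give rest periods of 14 and 21 days for the 200 mg 14-day and 7-day schedules.

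Other parts of the SAP allow for the shorter start. Section 6 accepts 14 actual dosing days as a full cycle for those assigned to it, and 9.9 counts by arm "Subjects who have been assigned to 300 mg x 14 days dose during Cycle 1 or Cycle 2". Sections 9.1 and 9.8 make no such allowance, and SAP Section 16 gives no reason.

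**The concern.** Relative dose intensity is normally read as the share of the planned dose that was delivered, with shortfalls put down to reductions, interruptions or missed doses. Here a subject can take every planned tablet and still show a shortfall, because the reference is a schedule that subject was not assigned.

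The two kinds of shortfall then cannot be told apart. The schedules 300 mg x 14 days and 200 mg x 21 days both average 150 mg/day. The category table would pool a planned shorter schedule with toxicity reductions, in both arms. The Protocol's risk assessment (1.4.1) presents the 14-day start as a measure against severe infection, so delivered dose under that start should be readable.

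**Working it through.** **Inputs.** Planned intensity 225 mg/day (SAP 9.8); closing rest 7 days (SAP 9.1); 14 dosing days in Cycles 1-2 (Protocol 8.2, 8.2.4). The rest after 300 mg x 14 days is not stated; 28 - 14 = 14 days is inferred. Cycles are taken as 28 days without delay, fully compliant, with no death during the closing rest.

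**Plan's own figure.** 300 x 21/28 = 225 mg/day. For k cycles of 21 days, cumulative dose is 6300k mg and duration is 28(k - 1) + 21 + 7 = 28k days. That is 225 mg/day, or 100% at every k. The SAP rules agree with each other for the 21-day schedule.

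**300 mg x 14 days throughout.** Dose = 4200k mg. SAP duration = 28(k - 1) + 14 + 7 = 28k - 7 days. RDI = [4200k/(28k - 7)]/225.

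| Cycles | Dose/duration | mg/day | RDI |
|---|---|---|---|
| 1 | 4200/21 | 200.0 | 88.9% |
| 2 | 8400/49 | 171.4 | 76.2% |
| 3 | 12600/77 | 163.6 | 72.7% |
| 6 | 25200/161 | 156.5 | 69.6% |
| 12 | 50400/329 | 153.2 | 68.1% |

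The limit is 150/225 = 66.7%.

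**Two 14-day cycles, then 21 days.** Dose = 8400 + 6300(k - 2) mg; duration = 28k days.

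- 3 cycles: 14700/84 = 175.0 mg/day, 77.8%
- 6 cycles: 33600/168 = 200.0 mg/day, 88.9%
- 12 cycles: 71400/336 = 212.5 mg/day, 94.4%

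**Separating the two rules (300 mg x 14 days throughout).**

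| Denominator | Closing rest | 1 cycle | 2 cycles | 6 cycles |
|---|---|---|---|---|
| 225 | 7 days (SAP) | 88.9% | 76.2% | 69.6% |
| 225 | 14 days | 66.7% | 66.7% | 66.7% |
| 150 | 7 days | 133.3% | 114.3% | 104.3% |
| 150 | 14 days | 100% | 100% | 100% |

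The denominator alone produces the low score. The short rest pushes the other way.

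**Duration and cycle length.** Duration is short by 14 - 7 = 7 days if the last cycle is on 14 days, by 21 - 7 = 14 days if on 7 days, and by nothing if on 21 days. For 14-day subjects, average cycle length is (28k - 7)/k: 21.0 days at one cycle, 24.5 at two and 26.8 at six, against 28.

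**Overlap with toxicity reductions.** A 21-day starter reduced to 200 mg x 21 days from Cycle 2 scores (6300 + 5 x 4200)/168/225 = 72.2% at six cycles. That is above the 69.6% of an unreduced, fully compliant 14-day subject.

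**The case against.** The strongest defence is that 225 mg/day is a deliberate common reference. The SAP applies it to all subjects, and Protocol 8.2.2 and SAP 4.1.2 still describe 21 days as the general schedule. The step-up also depends partly on the absence of Grade 3 or 4 toxicity requiring delay or reduction. A subject still on 14 days at Cycle 6 may be there because of toxicity, and scoring that subject 100% would hide it. This stands as a reason to keep a common-reference table, but not an unlabelled one. Evidence of hematological improvement also keeps subjects on 14 days, so the score cannot be read as toxicity either.

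The rest of the SAP covers part of the gap. Section 9.10 measures compliance against the intended dose and would show these subjects at 100%; 9.5 reports days dosed per cycle; 9.9 counts 14-day starters and reports adjustments with reasons. This stands, and it limits the harm.

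Three stronger readings are tempting. A reader might infer that both rules make compliant subjects look under-dosed; the rest rule raises intensity. A reader might infer that all 14-day starters fall below 75%; that takes at least three cycles wholly on 14 days, and fully compliant subjects who step up after Cycle 2 stay above it. A reader might call 225 an arithmetic slip; it is correct for the 21-day schedule, and the problem is applying it to everyone.

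**Conclusion.** The point holds. For subjects on the 14-day schedule, RDI as defined does not measure delivery of their planned dose: full compliance scores from 88.9% down towards 66.7% if they stay on 14 days, and 77.8% rising towards 100% if they step up after Cycle 2. Treatment duration and average cycle length are biased down for anyone whose last cycle is on 14 or 7 days.

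These sizes rest on the assumptions in the check, including the inferred 14-day rest for 300 mg x 14 days. Death within the closing rest shortens duration and raises the score on any schedule. The number of subjects affected is not given, so the shift in the category table cannot be estimated.

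The effect is confined to descriptive exposure summaries. Nothing in the documents links RDI to the efficacy analyses, alpha or power, and no view is taken on which schedule is clinically right.

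**What to change.** Change both rules together; the check shows that changing either alone gives a wrong value.

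- **SAP 9.1:** end treatment duration at last dose date + (28 - scheduled dosing days of the last cycle), or death if earlier. Average cycle length in 9.4 then follows.
- **SAP 9.8:** build planned intensity cycle by cycle from the protocol-planned schedule: 14 days where the subject was assigned the 300 mg x 14-day start, 21 days where assigned or stepped up to 21. State that toxicity-driven dose or schedule reductions do not lower the denominator. Otherwise a subject reduced from 300 to 200 mg x 14 days would be scored 100/100 = 100% rather than 100/150 = 66.7%, and RDI would largely duplicate 9.10.
- **Common reference:** if intensity against 300 mg x 21 days is also wanted, label it so and show it by the two starting-schedule groups in SAP 9.9.

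Protocol 8.2 can be read as putting everyone beyond Cycle 2 on 21 days, while 8.2.4 makes the increase conditional. These passages must be reconciled before the planned schedule is programmed.

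The cost is SAP wording and reprogramming of exposure tables, using assignment and dosing data that SAP 6 and 9.9 already rely on. The primary study report was final by 04-Feb-2020, so for that analysis this means a supplementary table. Protocol Appendix J also provides for an exposure summary in the Extension Phase, where the same definitions should apply.

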9.9. Dose Adjustment

Dose adjustment (reduction/interruption), as reported in the Study Drug Record CRF page, will be summarized by treatment group and include the following:

- Subjects with at least one dose adjustment
- Reason for dose adjustment
- Time to the first dose adjustment
- Time to the first dose adjustment due to AE
- Duration of the first dose adjustment due to AE

Subjects who have been assigned to 300 mg x 14 days dose during Cycle 1 or Cycle 2 and subjects who have not been assigned to 300 mg x 14 days dose during Cycle 1 or Cycle 2 will be identified and the number of subjects will be presented by treatment group.

For subjects who have not been assigned to 300 mg x 14 days dose during Cycle 1 or Cycle 2, the number of dose reductions will be identified and summarized by treatment group:

- Subjects with only one dose reduction (from 300 mg x 21 days to 200 mg x 21 days);
- Subjects with only two dose reductions (from 300 mg x 21 days to 200 mg x 21 days, then from 200 mg x 21 days to 200 mg x 14 days);
- Subjects with three dose reductions (from 300 mg x 21 days to 200 mg x 21 days, then from 200 mg x 21 days to 200 mg x 14 days, then from 200 mg x 14 days to 200 mg x 7 days).

9.10. Treatment Compliance

The compliance rate (%) for each subject will be computed as 100 times the cumulative dose (in mg) taken over the period divided by the intended cumulative dose (in mg) that should have been taken over the same period. It will be calculated for each subject for each treatment cycle and overall.

Treatment compliance will be summarized using descriptive statistics by cycle and overall. Additionally, for overall treatment compliance, the number and percentage of subjects will be summarized by category $< 75\%$, $\geq 75\%$ to $\leq 120\%$, and $> 120\%$.

10. EFFICACY ANALYSIS

All efficacy analysis will be performed on the ITT population. Key efficacy analysis will be performed on the mITT population as supportive evidence and to assess the robustness of the efficacy findings. Subjects will be analyzed according to randomized treatment group.

A sequential gate-keeping approach will be used to control the overall type I error rate and to perform hypothesis testing on multiple endpoints. Two endpoints, the primary efficacy endpoint of RBC transfusion independence and the key secondary endpoint of OS, will be tested sequentially in the pre-specified order. The primary efficacy endpoint will be tested first at the two-sided 0.05 significance level. In order to preserve the overall alpha level at 0.05 across the RBC transfusion independence and OS endpoints, formal statistical inference for the OS analyses can only be made if superiority of oral azacitidine is demonstrated for the primary efficacy endpoint, RBC transfusion independence, at the two-sided 0.05 significance level.

The primary efficacy endpoint, RBC transfusion independence, will be analyzed and reported only once after all 100% of the information is available for RBC transfusion independence rates (ie, after all 216 subjects have completed 12 months (52 weeks [364 days]) of double-blind treatment or have been discontinued from treatment). An interim analysis of the OS endpoint will also be conducted at the time of the analysis of the primary efficacy endpoint as the number of required 205 death events will not be reached by the time of the final analysis for the RBC transfusion independence endpoint. An O'Brien-Fleming group sequential type boundary will be used to preserve the overall alpha level of 0.05 for the analysis of OS.

The remaining secondary efficacy variables, with the exception of the proportion of subjects progressing to AML and time to AML progression, will be analyzed and reported once at the time of the analysis of RBC transfusion independence. Subjects will continue to be followed for progression to AML and survival until 205 deaths have been observed. Other than the pre-specified sequential testing of RBC transfusion independence and OS, no additional alpha adjustments for multiplicity will be made.

As there were no subjects enrolled from Japanese sites, the randomization stratification factor "country of enrollment (ie, Japan versus ROW)" will not be used when the analysis is performed.

10.1. Analysis of Primary Efficacy Endpoint

The primary efficacy endpoint of RBC transfusion independence is defined as the absence of any RBC transfusion during any consecutive "rolling" 56 days within the treatment period. A subject who did not receive any RBC transfusion during a consecutive rolling 56 days (i.e., day 1 to day 56, day 2 to day 57) will be considered as a 56-day RBC transfusion independent responder. Subjects without achieving the response as defined above, subjects with less than 56 days of assessment during the double-blind treatment period, and subjects who had average baseline RBC transfusion units less than 2 units per 28 days (as defined in Section 8.2) will be counted as non-responders.

All RBC transfusion records on or after randomization within the evaluation period will be used to assess the response for each subject. In other words, the days after the end of the evaluation period will not contribute to a rolling period. The end date of the evaluation period is defined as:

- For a subject who discontinues the treatment,

- If the subject doesn't receive a subsequent MDS treatment, use the date of end of treatment visit;
- If the subject receives a subsequent MDS treatment, use the start date of the subsequent MDS treatment – 1 day, or the date of end of treatment visit, whichever is earlier;
- For a subject who is still on-treatment at the time of the database lock for the primary analysis, the subject's latest available assessment date in the database (from AE, vital sign, local and central lab, study drug records, efficacy assessments) will be used.

The 56-day rolling period for the RBS transfusion independent assessment starts on the date of randomization.

Note if the interval between the last RBC transfusion in the evaluation period (if there is at least one RBC transfusion during the evaluation period) and the end date of the evaluation period is less than 56 days, this rolling period, which is less than 56 days, won't be considered as meeting the transfusion independence criteria even though there is no RBC transfusion in it. The day on which the transfusion is received will not contribute to the 56-day without receiving RBC transfusion rolling period.

The primary efficacy analysis will be performed on the ITT population and will compare the RBC transfusion independence rates in the two treatment groups. The number and percentage of subjects achieving RBC transfusion independence and corresponding 95% confidence intervals (CI) will be tabulated and presented by treatment group. A stratified Mantel-Haenszel (MH) chi-squared test, stratifying for average baseline RBC transfusion requirement (≤ 4 units versus > 4 units of RBC per 28 days), baseline platelet transfusion status (dependent or independent) and ECOG performance status (0 to 1 versus 2), at a two-sided alpha level of 0.05, will be used to compare the RBC transfusion independence rate between the two treatment groups. The p-value from the stratified MH chi-square test will be the confirmatory p-value for the test of the null hypothesis that the proportion of subjects achieving RBC transfusion independence is equal between the two treatment groups. Summaries will include the unadjusted difference in proportions between the two treatment groups with corresponding 95% CI and the common odds ratio with corresponding 95% CI. Subject listings with supporting data will be provided.

The stratification variables, average baseline RBC transfusion requirement (≤ 4 units versus > 4 units of RBC per 28 days), baseline platelet transfusion status (dependent or independent) and ECOG performance status (0 to 1 versus 2), will be derived from the corresponding CRF pages (see Section 8.2) and used in the stratified MH test.

The analysis of the primary endpoint will be repeated for the mITT population as the supportive analysis. Additionally, the following sensitivity analyses will be conducted after re-define the transfusion dependent subjects at baseline. Only the re-defined baseline RBC transfusion dependent subjects will be included in the sensitivity analyses:

- Re-define baseline RBC transfusion dependent subjects using the RBC transfusion data during the 56 days immediately preceding randomization, and only including RBC transfusion units that were given for a hemoglobin value ≤ 9.0 g/dL;
- Re-define baseline RBC transfusion dependent subjects using the RBC transfusion data during the 84 days immediately preceding randomization, and only including

RBC transfusion units that were given for a hemoglobin value ≤ 9.0 g/dL for 84 days, only subjects who were randomized under the original protocol and protocol amendment 1 are included;

For the sensitivity analyses, the pre-transfusion hemoglobin value collected on the Transfusion CRF will be used to assess the baseline transfusion dependency.

